**RXSIGHT, INC.****PROTOCOL NO. CSP-028****A SINGLE CENTER EXPLORATORY STUDY TO EVALUATE UNCORRECTED DISTANCE VISION AND QUALITY OF VISION AFTER LIGHT TREATMENTS OF AN IMPLANTED RXSIGHT LIGHT ADJUSTABLE LENS (RXLAL) WITH THE LIGHT DELIVERY DEVICE (LDD) IN SUBJECTS WITH PREOPERATIVE CORNEAL ASTIGMATISM****1 STUDY SYNOPSIS****STUDY OBJECTIVE**

The objective of this study is to evaluate uncorrected distance vision and quality of vision as measured by the McAlinden QoV questionnaire 3 months following the final lock-in treatment of an implanted RxSight Light Adjustable Lens (RXLAL) with the Light Delivery Device (LDD) in subjects with preoperative keratometric astigmatism. This is an exploratory study. No primary effectiveness endpoints will be defined.

**STUDY POPULATION**

The study population will consist of up to 150 eyes in up to 75 subjects with 0.50 to 3.00 D of pre-operative keratometric astigmatism implanted with the RxLAL. Approximately 1/2 of the study population should have  $\geq 0.50$  D and  $\leq 1.5$  D of preoperative keratometric astigmatism and approximately 1/2 of the study population should have  $> 1.5$  D and  $\leq 3.00$  D of preoperative keratometric astigmatism. At least 10 eyes should have  $> 2$  D of preoperative keratometric astigmatism.

**STUDY DESIGN**

A prospective, single center, randomized, exploratory clinical study will be conducted. Subjects will be followed for a 6-month period.

Patients who require cataract extraction and intraocular lens implantation will be screened for eligibility. If it is determined that the patient may be eligible to participate, study staff will explain the study purpose, procedures, risks/benefits and subject responsibilities to the potential participant. Written informed consent will be obtained prior to any study specific testing. The patient is enrolled upon signing the informed consent. If both eyes of a patient meet study eligibility, a pre-determined randomization scheme will be utilized to designate each of the patient's eyes as the primary eye or the fellow eye. If only one eye of a patient meets study eligibility, that eye will automatically be designated as the primary eye.

At 3 weeks post-implantation, eyes will be refracted, undergo visual testing, and receive a power adjustment based on the manifest refraction. Subjects will return 3 to 7 days after their adjustment and the same measurements performed again. Depending on the adjustment(s) performed, subjects will receive one to three adjustments and one or two lock-in treatments.

Postoperatively, subjects will undergo complete ophthalmic examinations at regular intervals over a 6-month period.

Uncorrected distance visual acuity (UCDVA) and responses from the Quality of Vision (QoV) questionnaire will be summarized. All ocular adverse events (device related and unrelated) during the conduct of the study will be reported. All Secondary Surgical Interventions (SSIs) in study eyes during the conduct of the study will also be reported.

Both eyes of all subjects should be screened for eligibility.

#### **INCLUSION CRITERIA**

- Must sign a written Informed Consent form and be willing to undergo cataract surgery for unilateral or bilateral implantation of the RxLAL.
- Between the ages of 40 and 80 inclusive on the day the cataract surgery is performed.
- Study eye must have preoperative keratometric cylinder of  $\geq 0.50$  D and  $\leq 3.00$  D .
- Study eye must have cataract causing reduction in best corrected distance visual acuity (BCDVA) to a level of 20/32 or worse with or without a glare source.
- Study eye must have best corrected distance visual acuity projected (by clinical estimate based upon past ocular history or retinal exam) to be 20/20 or better after cataract removal and IOL implantation.
- If only one subject eye is enrolled in the study, the non-study eye must have potential for BCDVA of 20/40 or better after cataract removal and IOL implantation.
- Study eye has clear intraocular media other than cataract.
- Willing and able to comply with the requirements for study specific procedures and visits.
- Study eye has a dilated pupil diameter of  $\geq 7.0$  mm.
- Study eye requires an IOL power within the range available for the RxLAL.

#### **EXCLUSION CRITERIA**

- Study eye with zonular laxity or dehiscence.
- Study eye with pseudoexfoliation.
- Study eye with age-related macular degeneration involving the presence of geographic atrophy or soft drusen.
- Study eye with retinal degenerative disorder or macular disorder (other than mild macular degeneration) that is expected to cause future vision loss.
- Study eye with diabetes with any evidence of retinopathy.
- Study eye with evidence of glaucomatous optic neuropathy.
- Study eye with history of uveitis.

- Study eye with significant anterior segment pathology, such as rubeosis iridis, aniridia, or iris coloboma.
- Study eye with corneal pathology that is either progressive or sufficient to reduce BCDVA to worse than 20/20.
- Study eye with keratoconus or suspected of having keratoconus.
- Study eye with prior history of Intacs, Radial keratotomy (RK), Conductive keratoplasty (CK), Astigmatic keratotomy (AK), Phakic Implantable Collamer Lens (ICL), Corneal Inlay, or with previous pterygium excision unless the pterygium did not extend more than 2mm onto the cornea from the limbus.
- Study eye with clinically significant dry eye syndrome (DES).
- Study eye with clinically significant corneal haze.
- Study eye with clinically significant corneal opacity.
- Serious co-morbid conditions that in the judgment of the investigator makes inclusion in the study not in the best interest of the subject.
- Subjects taking systemic medication that may increase sensitivity to UV light such as tetracycline, doxycycline, psoralens, amiodarone, phenothiazines, chloroquine, hydrochlorothiazide, hypericin, ketoprofen, piroxicam, lomefloxacin, and methoxsalen. LDD treatment in patients taking such medications may lead to irreversible phototoxic damage to the eye. This is only a partial list of photosensitizing medications. Please evaluate all medications that the patient is taking for this effect prior to consideration for implantation.
- Subjects taking a systemic medication that is considered toxic to the retina such as tamoxifen.
- Study eye with irregular astigmatism.
- Study eye with history of ocular herpes simplex virus.
- Study eye with history of a congenital color vision defect.

## OUTCOME PARAMETERS

### Exploratory Effectiveness Parameter:

- Percent of eyes with UCDVA of 20/20 or better at 6 Months Postop (3 Months Post Lock-In)

Exploratory effectiveness analyses will be based on the 6-month UCDVA of eyes successfully implanted with the RxLAL.

### Safety Parameters:

The following safety parameters will be evaluated at 6 Months Postop (3 Months Post Lock-In):

- Ocular adverse events (device related and unrelated) of the study eyes that occur during the conduct of the study.

- Secondary Surgical Interventions (SSIs) of the study eyes that occur during the conduct of the study.

Subjects who agree to participate in the study will return for the listed follow-up examinations for each study eye:

**Examination Schedule:**

Evaluation	
Preoperative	Day -60 to Day -1
Operative	Day 0, day of surgery
Postop Day 1	Days 1 to 2 postop
Postop Week 1	Days 7 to 14 postop
Postop Week 3	Days 17 to 24 postop: Adjustment #1
Adjustment #2, if needed	3 to 7 days post Adjustment #1
Adjustment #3, if needed	3 to 7 days post Adjustment #2
Lock-in #1	3 to 7 days post final adjustment
Lock-in #2, if needed	3 to 7 days post lock-in #1
Post Lock-In	3 to 7 days post final lock-in
1 Month Post Lock-In	30 to 60 days post final lock-in
3 Months Post Lock-In/6 Months Postop	Days 120 to 180 postop

**Clinical Parameters:**

Clinical assessments when indicated will be performed in the following order:

1. Quality of Vision (QoV) questionnaire
2. Demographics
3. Ocular history including medications
4. Ocular Biometry: ACD and axial length (Optical biometry only)
5. Autorefraction
6. Corneal Keratometry
7. Vision Quality Measurement (HD Analyzer)
8. Subjective symptoms/complaints (subject reported)
9. Uncorrected distance visual acuity (UCDVA) Monocular
10. Manifest Refraction

13. City University Color Test
14. Intraocular pressure
15. Dilated pupil diameter
16. Slit Lamp Examination

17. Fundus Exam

18. Adverse Events

## ABBREVIATIONS AND DEFINITION OF TERMS

AE	Adverse Event
AK	Astigmatic Keratotomy
ANSI	American National Standards Institute
BCDVA	Best Corrected Distance Visual Acuity
CI	Confidence Interval
CK	Conductive Keratoplasty
CRF	Case Report Form
D	Diopter
DES	Dry Eye Syndrome
ETDRS	Early Treatment Diabetic Retinopathy Study
GCP	Good Clinical Practice
ICH	International Conference on Harmonization
ICL	Phakic Implantable Collamer Lens
IOL	Intraocular Lens
IOP	Intraocular Pressure
LASIK	Laser Assisted In-Situ Keratomileusis
LD D	Light Delivery Device
MR	Manifest Refraction
MRCYL	Manifest Refraction Cylinder
MRSE	Manifest Refraction Spherical Equivalent
OD	Right eye
OS	Left eye
PCO	Posterior Capsular Opacity
PI	Principal Investigator
RxLAL	RxSight Light Adjustable Lens
SAE	Serious Adverse Event
SD	Standard Deviation
SE	Spherical Equivalent
UCDVA	Uncorrected Distance Visual Acuity

## 2 INTRODUCTION AND RATIONALE

In modern cataract surgery, spectacle freedom for the patient, either for distance vision, near vision, or both, is becoming more important. Globally, key cataract technology advancements (e.g.; monofocal, toric, and foldable IOLs; ultrasound, optical and intraoperative biometry; phacoemulsification and femtosecond laser assisted surgery), have resulted in important reductions in residual refractive error and improved uncorrected distance visual acuity (UCDVA), both of which are highly correlated with patient satisfaction following cataract surgery.

However, while the potential for significant post-operative residual refractive error has been reduced, it remains the most frequent cataract surgery complication. Approximately 30-60% of patients undergoing monofocal IOL implantation and 15-30% of patients undergoing toric IOL procedures require spectacle correction for distance correction as a result of a non-emmetropic refraction. The large majority of these patients have residual refractive errors that are less than 2 D of magnitude.

The major causes for residual refractive error following cataract surgery include:

- Estimation errors for postoperative IOL position, preoperative axial length measurement and limitations of IOL calculation formulas that affect both spherical and toric IOLs.
- Pre-existing corneal astigmatism (reported to exceed 1.00 D in approximately one-third of cataract patients) and imprecise preoperative measurement of corneal astigmatism.

 Nordan, LT. *The Surgical Rehabilitation of Vision*. Gower Medical, New York, 1991.

RxSight addresses the problem of residual refractive error with an IOL for which spherical and cylindrical power can be adjusted post-implantation. Following surgical implantation and a period of post-operative stabilization, patients return for examination and refractive adjustment in the office using a profiled beam of light from the Light Delivery Device (LDD). By producing the desired change in lens curvature and spherocylindrical power of the implanted RxSight Light Adjustable Lens (RxLAL), this approach can obviate the need for secondary surgical procedures for the vast majority of patients with residual refractive error.

## **2.1 CLINICAL STUDIES PERFORMED WITH THE LIGHT ADJUSTABLE LENS AND LIGHT DELIVERY DEVICE**

### **U.S. Phase III Study**

A 600 eye prospective, randomized, controlled, multi-center clinical trial of the LAL and LDD designed to evaluate safety and effectiveness over a 12-month period was conducted at 17 sites in the United States under an Investigational Device Exemption. In addition to the visual correction of aphakia, reduction in residual spherocylindrical refractive error and improvement in uncorrected distance visual acuity were evaluated following LAL implantation and subsequent refractive adjustment of the LAL by the LDD.

Eyes with  $\geq 0.75$  and  $\leq 2.5$  diopters (D) of keratometric cylinder were randomly assigned to receive either the LAL or a commercially available, posterior chamber, non-accommodating, control monofocal IOL. Six hundred eyes were implanted with 403 eyes randomized to the LAL group and 197 eyes to the Control group.

Co-primary effectiveness endpoints included percent reduction in manifest cylinder, percent mean absolute reduction in manifest refraction spherical equivalent (MRSE), and rotation of

---

the LAL. All primary effectiveness endpoints compared pre-adjustment (LAL) or 17-21 days (Control) to 6 months postoperatively and the first two endpoints compared results between the LAL and Control groups. All three co-primary effectiveness endpoints were met with a p-value <0.0001. The difference in means for percent reduction in manifest cylinder was 54.7%, with a p-value <0.0001. The difference in means for percent reduction in absolute MRSE was 41.1% with a p-value <0.0001. Rotation of the LAL of  $\leq 5$  degrees was observed in 96.1% of LAL implanted eyes with both the upper and lower bound of the 95% confidence interval exceeding the requirement of 90%.

100% of eyes in both the LAL and Control groups had BCDVA of 20/40 or better, exceeding the historic grid rate of 92.5% (ISO 11979-7).

### **OUS Clinical Evaluations**

Other clinical evaluations have been conducted outside the United States to study the effectiveness and safety of spherical and spherocylindrical light treatment profiles of the LAL in aphakic patients.

In a post-CE mark study published by Hengerer et al. of 122 LAL eyes with eighteen months follow-up in Bochum, Germany, the authors reported 88% of eyes achieving a UCDVA of 20/20 or better and 98% of eyes within 0.50 diopters of their intended target refraction at 18 months after lock-in treatment. 100% of the eyes met the  $\geq 20/40$  BCDVA safety criteria.

In summary, clinical evaluations have demonstrated that the Light Adjustable Lens and Light Delivery Device provide a predictable, stable, and safe treatment of aphakia in patients in whom the cataractous natural lens has been removed by phacoemulsification and who wish to minimize their postoperative spherical/spherocylindrical refractive error and improve their uncorrected distance visual acuity.

---

### 3 STUDY OBJECTIVE

The objective of this study is to evaluate uncorrected distance vision and quality of vision as measured by the McAlinden QoV questionnaire 3 months following the final lock-in treatment of the implanted RxSight Light Adjustable Lens (RxLAL) with the Light Delivery Device (LDD) in subjects with preoperative keratometric astigmatism. This is an exploratory study. No primary effectiveness endpoints will be defined.

### 4 STUDY DESIGN

A prospective, single center, randomized, exploratory clinical study will be conducted. Subjects will be followed for a 6-month period.

Patients who require cataract extraction and intraocular lens implantation will be screened for eligibility. If it is determined that the patient may be eligible to participate, study staff will explain the study purpose, procedures, risks/benefits and subject responsibilities to the potential participant. Written informed consent will be obtained prior to any study specific testing. The patient is enrolled upon signing the informed consent. If both eyes of a patient meet study eligibility, a pre-determined randomization scheme will be utilized to designate each of the patient's eyes as the primary eye or the fellow eye. If only one eye of a patient meets study eligibility, that eye will automatically be designated as the primary eye.

At 3 weeks post-implantation, eyes will be refracted, undergo visual testing, and receive a power adjustment based on the manifest refraction. Subjects will return 3 to 7 days after their adjustment and the same measurements performed again. Depending on the adjustment(s) performed, subjects will receive one to three adjustments and one or two lock-in treatments.

Postoperatively, subjects will undergo complete ophthalmic examinations at regular intervals over a 6-month period.

Uncorrected distance visual acuity (UCDVA) and responses from the Quality of Vision (QoV) questionnaire will be summarized. All ocular adverse events (device related and unrelated) during the conduct of the study will be reported. All Secondary Surgical Interventions (SSIs) in study eyes during the conduct of the study will also be reported.

### 5 OUTCOME PARAMETERS

#### 5.1 EXPLORATORY EFFECTIVENESS PARAMETERS

- Percent of eyes with UCDVA of 20/20 or better at 6 Months Postop (3 Months Post Lock-In)

Exploratory effectiveness analyses will be based on the 6-month UCDVA of eyes successfully implanted with the RxLAL.

#### 5.2 SAFETY PARAMETERS

The following safety parameters will be evaluated at 6 Months Postop (3 Months Post Lock-In):

- Ocular adverse events (device related and unrelated) of the study eyes during the conduct of the study.
- Secondary Surgical Interventions (SSIs) of the study eyes during the conduct of the study.

## 6 STUDY POPULATION

The study population will consist of up to 150 eyes in up to 75 subjects with 0.50 to 3.00 D of pre-operative keratometric astigmatism implanted with the RxLAL. Approximately 1/2 of the study population should have  $\geq 0.50$  D and  $\leq 1.5$  D of preoperative keratometric astigmatism and approximately 1/2 of the study population should have  $> 1.5$  D and  $\leq 3.00$  D of preoperative keratometric astigmatism. At least 10 eyes should have  $> 2$  D of preoperative keratometric astigmatism.

Both eyes of all subjects should be screened for eligibility.

### 6.1 INCLUSION CRITERIA

- Must sign a written Informed Consent form and be willing to undergo cataract surgery for unilateral or bilateral implantation of the RxLAL.
- Between the ages of 40 and 80 inclusive on the day the cataract surgery is performed.
- Study eye must have preoperative keratometric cylinder of  $\geq 0.50$  D and  $\leq 3.00$  D.
- Study eye must have cataract causing reduction in best corrected distance visual acuity (BCDVA) to a level of 20/32 or worse with or without a glare source.
- Study eye must have best corrected distance visual acuity projected (by clinical estimate based upon past ocular history or retinal exam) to be 20/20 or better after cataract removal and IOL implantation.
- If only one subject eye is enrolled in the study, the non-study eye must have potential for BCDVA of 20/40 or better after cataract removal and IOL implantation.
- Study eye has clear intraocular media other than cataract.
- Willing and able to comply with the requirements for study specific procedures and visits.
- Study eye has a dilated pupil diameter of  $\geq 7.0$  mm.
- Study eye requires an IOL power within the range available for the RxLAL.

### 6.2 EXCLUSION CRITERIA

- Study eye with zonular laxity or dehiscence.
- Study eye with pseudoexfoliation.
- Study eye with age-related macular degeneration involving the presence of geographic atrophy or soft drusen.

- Study eye with retinal degenerative disorder or macular disorder (other than mild macular degeneration) that is expected to cause future vision loss.
- Study eye with diabetes with any evidence of retinopathy.
- Study eye with evidence of glaucomatous optic neuropathy.
- Study eye with history of uveitis.
- Study eye with significant anterior segment pathology, such as rubeosis iridis, aniridia, or iris coloboma.
- Study eye with corneal pathology that is either progressive or sufficient to reduce BCDVA to worse than 20/20.
- Study eye with keratoconus or suspected of having keratoconus.
- Study eye with prior history of Intacs, Radial keratotomy (RK), Conductive keratoplasty (CK), Astigmatic keratotomy (AK), Phakic Implantable Collemer Lens (ICL), Corneal Inlay, or with previous pterygium excision unless the pterygium did not extend more than 2mm onto the cornea from the limbus.
- Study eye with clinically significant dry eye syndrome (DES).
- Study eye with clinically significant corneal haze.
- Study eye with clinically significant corneal opacity.
- Serious co-morbid conditions that in the judgment of the investigator makes inclusion in the study not in the best interest of the subject.
- Subjects taking systemic medication that may increase sensitivity to UV light such as tetracycline, doxycycline, psoralens, amiodarone, phenothiazines, chloroquine, hydrochlorothiazide, hypericin, ketoprofen, piroxicam, lomefloxacin, and methoxsalen. LDD treatment in patients taking such medications may lead to irreversible phototoxic damage to the eye. This is only a partial list of photosensitizing medications. Please evaluate all medications that the patient is taking for this effect prior to consideration for implantation.
- Subjects taking a systemic medication that is considered toxic to the retina such as tamoxifen.
- Study eye with irregular astigmatism.
- Study eye with a history of ocular herpes simplex virus.
- Study eye with a history of a congenital color vision defect.

[figure not shown]

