## 7.2 SUBJECT ENTRY

Patients who require cataract extraction and intraocular lens implantation will be screened for eligibility. If it is determined that the patient may be eligible to participate, study staff will explain the study purpose, procedures, risk/benefits and subject responsibilities to the potential participant. Written informed consent will be obtained prior to any study specific testing. The patient is enrolled upon signing the informed consent. The subject will sign and date the informed consent form in the presence of the person conducting the consent process. The investigator and/or the person conducting the consent process will also sign and date the consent form. The preoperative examination will be performed no more than 90 days prior to surgery. If the 90-day time period elapses, it is acceptable for patients to be re-screened by undergoing a complete preoperative examination. If both eyes of a patient meet study eligibility, a pre-determined randomization scheme will be utilized to designate each of the patient's eyes as the primary eye or the fellow eye. If only one eye of a patient meets study eligibility, that eye will automatically be designated as the primary eye.

Only subjects meeting all inclusion/exclusion criteria will be implanted. Those subjects who do not meet the inclusion/exclusion requirements will be considered screen failures. Subjects will continue to be enrolled until approximately 150 eyes in about 75 subjects have undergone implantation. Unique identification numbers will be assigned to each subject.

Study enrollment will be tracked to ensure that approximately 1/2 of the study population will have  $\geq 0.50$  D to  $\leq 1.5$  D of preoperative keratometric astigmatism and approximately 1/2 of the study population will have  $>1.5$  D to  $\leq 3.00$  D of preoperative keratometric astigmatism. At least 10 eyes should have  $>2$  D of preoperative keratometric astigmatism. Implantations in one bin may be suspended to ensure enrollment in all bins meets these requirements.

The implant lens power for the RxLAL will be calculated based upon the ocular biometry data and a lens power formula of the surgeon's choice with a postoperative spherical

equivalent (SE) outcome closest to emmetropia. If both eyes of a patient are enrolled, the primary eye will be scheduled for implantation prior to the fellow eye.

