### **7.3.2 LIGHT TREATMENT PROCEDURE**

Seventeen (17) to 24 days after surgery, the subject will return for the Postop Week 3 evaluation and a 1st adjustment treatment of the RxLAL. Subsequent second and third adjustment treatments, if necessary, will all be separated by 3-7 days. The necessity of the second adjustment treatment is guided by the LDD.

Otherwise proceed to lock-in #1 treatment. The subject will receive the 1st lock-in treatment 3-7 days after the final adjustment treatment. If necessary, lock-in #2 may be performed 3-7 days after lock-in #1. Depending on the adjustment(s) performed, subjects will receive one to three adjustments and one or two lock-in treatments.

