#### **7.3.2.1 Postponement of Light Treatment Procedure(s)**

LDD treatment should be delayed if any of the following new symptoms or changes in performance are noted;

- [REDACTED]
- [REDACTED]
- Best Corrected Distance Visual Acuity: With any loss of BCDVA (unless the cause is known to be non-retinal) of 10 letters or more on an ETDRS (logMAR) chart, treatment should be delayed.

[REDACTED]

- If sutures were utilized at the time of surgery to close the incision wound, light treatments should not commence on the study eye until a minimum of 4 weeks after suture removal.
- A study eye with an ocular adverse event that could be negatively impacted by light treatment or negatively impact the effectiveness or safety of a light treatment should have light treatments delayed until after the adverse event has subsided. This includes corneal edema and superficial punctate keratitis (SPK) (Grade 3 (moderate) or more severe)), retinal conditions including diabetic retinopathy and cystoid macular edema, epithelial defect, and endophthalmitis.
- If a study eye is discovered with evidence of premature photopolymerization as evidenced as a zone on the lens surface, the investigator should contact the Sponsor for further instructions. (see [REDACTED] for additional details regarding premature photopolymerization).
- Any study eye possessing clinically significant posterior capsular (PC) haze should undergo a YAG capsulotomy procedure prior to the adjustment. A minimum of 48 hours should separate the YAG treatment from the corresponding refraction and LDD adjustment.

---

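### The photosensitizing-drug review is timed before implantation, but the hazard it guards against is LDD treatment on Days 17 to 52, and the treatment steps in 7.3.2.2 to 7.3.2.4 include no medication check

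*Combined protocol and SAP*

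**What the plan says.** Section 6.2 of the combined protocol and SAP excludes subjects on systemic drugs that raise sensitivity to UV light. Its list, described as partial, includes doxycycline and hydrochlorothiazide. The reason given is the light treatment itself: "LDD treatment in patients taking such medications may lead to irreversible phototoxic damage to the eye". The instruction that follows sets the timing: "Please evaluate all medications that the patient is taking for this effect prior to consideration for implantation".

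Section 7.2 applies eligibility at surgery: "Only subjects meeting all inclusion/exclusion criteria will be implanted". For bilateral subjects it adds: "If both eyes of a patient are enrolled, the primary eye will be scheduled for implantation prior to the fellow eye".

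Section 7.3.2 places the first adjustment later: "Seventeen (17) to 24 days after surgery, the subject will return for the Postop Week 3 evaluation". It also sets the number of treatments: "subjects will receive one to three adjustments and one or two lock-in treatments". Successive treatments are 3 to 7 days apart.

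Section 7.3.2.1 lists reasons to postpone, introduced by: "LDD treatment should be delayed if any of the following new symptoms or changes in performance are noted". The readable reasons are loss of best corrected acuity, sutures, certain ocular adverse events, premature photopolymerization and posterior capsular haze. Other entries are redacted. Section 7.5 lists an ocular history that covers medications as assessment 3. Its visits are set in Table 2, whose body is not shown.

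**The concern.** The control and the hazard sit at different times. The drug review comes before surgery, while the exposure that makes the drug dangerous begins more than two weeks after it. A subject who is prescribed doxycycline or hydrochlorothiazide after Day 0, perhaps by a prescriber outside the study, was properly eligible. If only the stated timing is followed, that subject could receive UV treatment in exactly the situation section 6.2 warns about.

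Eligibility cannot correct this after surgery. Section 7.7.4 allows discontinuation after implantation only for explantation or death, so protection has to come from a rule about treatment. Adverse event records are not a reliable substitute. Section 9.2.1 requires ocular events and serious systemic events to be documented, so a non-serious systemic illness treated with such a drug need not appear.

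What is at stake is the safety of individual subjects. The harm named is irreversible, and section 9.2.5 separately lists possibly permanent UV damage to the cornea and retina as a risk of this lens.

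**Working it through.** The plan states no figure for the interval between drug review and light exposure, so there is none to reproduce. The interval follows from the visit windows.

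**Inputs**
- First adjustment: Day 17 to 24 (7.3.2 and 7.4).
- Gap between successive treatments: 3 to 7 days (7.3.2 and 7.4).
- Adjustments a = 1 to 3; lock-ins l = 1 or 2 (7.3.2).
- Preoperative examination: Day -90 to -1 (7.2 and 7.4). The synopsis schedule has Day -60 to -1.

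**Exposures per eye:** a + l, from 1 + 1 = 2 to 3 + 2 = 5.

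**Day of last exposure, on schedule.** After the first adjustment there are k = (a - 1) + l further treatments, so the last falls between 17 + 3k and 24 + 7k:
- 1 adjustment, 1 lock-in (k = 1): Day 20 to 31
- 1 + 2 or 2 + 1 (k = 2): Day 23 to 38
- 2 + 2 or 3 + 1 (k = 3): Day 26 to 45
- 3 + 2 (k = 4): Day 29 to 52

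The overall range is Day 20 to Day 52.

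**Time from drug review to exposure, if the review is done at the preoperative examination (assumption)**
- To the first exposure: 1 + 17 = 18 days to 90 + 24 = 114 days.
- To the last exposure: 1 + 20 = 21 days to 90 + 52 = 142 days.
- With the synopsis window, the maxima are 60 + 24 = 84 and 60 + 52 = 112 days.
- If drug status is instead current on Day 0, the interval to the last exposure is 20 to 52 days.

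**Departures from schedule.** Postponement lengthens these intervals. For a sutured eye, "light treatments should not commence on the study eye until a minimum of 4 weeks after suture removal", which is at least 4 x 7 = 28 days after removal.

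**Bilateral subjects.** The unit is the eye. With g days between surgeries (not given in the documents), the fellow eye's last exposure falls g + 20 to g + 52 days after the primary eye's surgery. The fellow eye has its own Day 0, and eligibility applies again at its implantation.

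**Search for a later check.** Section 7.3.2.2 requires the protocol measurements and adequate dilation before treatment. Sections 7.3.2.3 and 7.3.2.4 cover data entry, anesthetic, contact lens, alignment, irradiation and eyewear. Redactions in these three sections are few, and none of the readable steps asks about medication.

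**Comparison within the plan.** Diabetic retinopathy is an exclusion in 6.2 and also a reason to delay light treatment in 7.3.2.1. For that condition the plan does not rely on screening alone. Photosensitizing drugs, whose exclusion is justified by the light treatment itself, have no readable counterpart.

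**The case against.** The strongest objection is that the place where a drug rule would sit is partly blacked out. The first two items of 7.3.2.1 are redacted, as is a block after the acuity item. The lead-in speaks of symptoms and performance, but readable items such as sutures go beyond that, so it does not rule out a medication item. Table 2 may place assessment 3 at every treatment visit, and 7.3.2.2 requires protocol measurements to be finished before treatment. The assessment-technique document and the LDD Operator's manual are also unavailable. This stands. A reader might infer that the plan has no postponement rule for these drugs; the documents do not support that, because redacted text is not missing text. What can be said is narrower: the stated review is timed before implantation, and the treatment steps name no check. Even if assessment 3 is repeated, no readable text says that it covers systemic drugs or links it to withholding light.

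Second, the 6.2 warning names LDD treatment, so the investigator has been told of the danger. That is true and lowers the severity. But the warning is worded as an entry criterion, and an investigator who is not told to ask again may not learn of a new prescription.

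Third, the intervals restate the treatment schedule and do not measure harm. That is correct. The documents give no rate of starting such drugs and no risk per exposure, so no probability can be quoted.

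**Conclusion.** The point holds as a timing mismatch. The stated drug review precedes implantation, while each eye's 2 to 5 UV exposures run, on schedule, from Day 17 to 24 until Day 20 to 52. Counted from a review at the preoperative examination, the last exposure comes 21 to 142 days later. That range rests on the assumption about where the review is done and on the 90-day window; with the synopsis window the upper end is 112 days.

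Severity is low to moderate and confidence is medium. Screening before implantation is sensible, because implantation commits the subject to light treatment, but it does not cover a change of medication afterwards. Two stronger conclusions should be avoided: that a postponement rule has been shown to be absent, and that 20 to 52 days, or 142 days, is a measure of risk. No effectiveness analysis is affected.

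**What to change.** First, the sponsor should confirm whether the redacted 7.3.2.1 items, Table 2, the assessment-technique document or the LDD Operator's manual already cover the point. Then:

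1. In 7.3.2.2, require the site to ask about new systemic medications of the kind listed in 6.2 before each adjustment and each lock-in. If Table 2 already places assessment 3 at those visits, use it and state that it includes these drugs.
2. Unless a redacted item already does so, add to 7.3.2.1 that LDD treatment is held while the subject is taking such a drug, with prompt sponsor contact about stopping or substituting it. If it cannot be stopped, require a documented risk-benefit decision by the investigator and sponsor, so that the hold is not open-ended.

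The cost is one question at 2 to 5 visits per eye that are already scheduled, plus one postponement item. The downside is an occasional delayed treatment. The subject then wears UV-protective eyewear longer, since 7.3.2.4 ends it 24 hours after the last lock-in. The lens also stays unlocked longer, and 9.2.5 warns that stray UV in that period can change vision. That is why a prompt decision belongs in the rule.
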